3 SAMPLE SIZE

This is a single center study conducted at 1 site and will enroll up to approximately 88 subjects.

This sample size accommodates withdrawal of consent or replacement for other non-TEAE reasons and is appropriate for dose escalation studies of this nature.

4 RANDOMIZATION

SAD cohorts:

- For each cohort (Level 1-5), 6 subjects will be randomized to receive MTR-601 and 2 subjects will be randomized to receive placebo.
- The SAD cohorts will be randomized 1:1 for sentinels and remaining 6 subjects in each cohort will be randomized 5:1 to receive MTR-601 or placebo. All SAD dose cohorts (including Level 2, Two-Dose) will have 2 sentinel subjects followed at least 72 hours later by the remaining 6 subjects.

In addition to the randomization scheme, there are also some specific instructions for the SAD Level 2, Two-Dose level cohort:

- For the first dose, subjects will be fasting.
- For the second dose, subjects will be fed state (standard not-high fat breakfast) 30 minutes before dosing.

MAD cohorts:

- For each cohort (Level 1-6), 6 subjects will be randomized to receive MTR-601 and 2 subjects will be randomized to receive placebo.

There are no sentinels in the MAD cohorts.

Cohort Type	Sentinels	Remaining Subjects
SAD	1:1	5:1
MAD	0	6:2

Subjects will be assigned to randomized treatment by the unblinded pharmacist in a sequential manner using the pre-determined randomization schedule. Subjects, the Sponsor study team, and the Investigator/site staff will be blinded to treatment assignment until after the final subject has completed the study. Unblinded personnel include site pharmacist (or designee), the unblinded pharmacy monitor (to ensure study drug accountability), and the Sponsor's unblinded team.

QMD Ref: Worldwide-TMP-ST-054-1.0_Effective: 12Aug2022	Governing QMD: Worldwide-SOP-ST-026
Confidentiality Statement This document is the property of Worldwide Clinical Trials Inc. and may not be duplicated, copied, altered or removed from company without prior approval from Worldwide Quality Assurance or in compliance with Worldwide Standard Operating Procedures.	

Worldwide Clinical Trials Controlled Quality Management Document			
		Sponsor:	MTR-601-NHV-101
		Protocol Number:	Motric Bio
STATISTICAL ANALYSIS PLAN			

5 PLANNED ANALYSES

The Statistical Analysis Plan (SAP) and Table, Figure, Listing (TFL) Shells (and any amendments) must be approved prior to database lock / breaking of the blind for analysis. If post database lock, additional statistical analyses or changes to the statistical analysis are required, then those will be documented in a Post Database Lock Statistical Analysis Plan Addendum.

5.1 Analysis Population

The following populations are defined for the purposes of analysis.

5.1.1 Enrolled Population

The Enrolled Set includes all subjects screened / who gave informed consent.

5.1.2 Safety Population

Includes all subjects who received at least one dose of MTR-601 or placebo. This is the primary population for exposure and safety analyses.

5.1.3 Pharmacodynamic Population

Includes all subjects who received at least one dose of MTR-601 or placebo and have at least one post-baseline pharmacodynamic assessment. This is the primary population for pharmacodynamic endpoints.

5.1.4 Pharmacokinetic (PK) Population

Includes all subjects who received study treatment and have sufficient MTR-601 plasma concentration data to estimate at least one of the planned PK parameters. All such subjects will be evaluated for PK unless major protocol deviations may have affected the data or if key dosing information is missing. This is the primary population for PK analysis.

5.2 Derived Data

This section describes the derivations required for statistical analysis. Unless otherwise stated, variables derived in the source data will not be re-calculated.

5.2.1 Age

Age in years at informed consent will be calculated using SAS function as

Age (years) = floor((intck('month', birthdate, date) - (day(date) < day(birthdate))) / 12)

QMD Ref: Worldwide-TMP-ST-054-1.0_Effective: 12Aug2022	Governing QMD: Worldwide-SOP-ST-026
Confidentiality Statement This document is the property of Worldwide Clinical Trials Inc. and may not be duplicated, copied, altered or removed from company without prior approval from Worldwide Quality Assurance or in compliance with Worldwide Standard Operating Procedures.	

Worldwide Clinical Trials Controlled Quality Management Document			
		Sponsor:	MTR-601-NHV-101
		Protocol Number:	Motric Bio
STATISTICAL ANALYSIS PLAN			

5.2.2 Race

Where more than one race category has been selected for a subject, these race categories will be combined into a single category labelled “Multiple Race” in the summary tables. The listings will reflect the original selected categories.

5.2.3 Baseline

Baseline is defined as the last non-missing value (either scheduled, unscheduled or repeat) before the subject receives the first dose of study drug.

For Cohort level 2, variables that will be summarized by treatment, the baseline for each dosing period is defined as the last non-missing value (either scheduled, unscheduled or repeat) that is collected before dosing for the relevant dosing period.

5.2.4 Duration / Study Day / Time

Study day will be calculated as the number of days from first dose of study drug.

- date of event – date of first dose of study drug + 1, for events on or after first dose
- date of event – date of first dose of study drug, for events before first dose

5.2.5 Conventions for Missing and Partial Dates

It is not expected that there will be any missing dates for events occurring during study conduct. Historical dates such as dates of medical history or prior medications may be missing or partial. Dates (historical or during study conduct) will only be imputed if a full date is needed for a calculation or to support a definition.

All dates presented in the individual subject listings will be as recorded on the Electronic Case Report Form (eCRF).

5.2.5.1 Missing Adverse Events Dates

In the rare case that an Adverse Event (AE) start date or time is missing and it is unclear whether the AE is treatment emergent or not then a conservative approach will be taken, and it will be assumed that the AE is treatment emergent and occurred after first dosing. If an adverse event stop date is missing it will be assumed that the AE is ongoing.

5.2.6 Exposure to Study Drug

Exposure to study drug will be calculated (in days) as follows from the date of last dosing minus the first day of dosing + 1.

QMD Ref: Worldwide-TMP-ST-054-1.0_Effective: 12Aug2022	Governing QMD: Worldwide-SOP-ST-026
Confidentiality Statement This document is the property of Worldwide Clinical Trials Inc. and may not be duplicated, copied, altered or removed from company without prior approval from Worldwide Quality Assurance or in compliance with Worldwide Standard Operating Procedures.	

Worldwide Clinical Trials Controlled Quality Management Document			
		Sponsor:	MTR-601-NHV-101
		Protocol Number:	Motric Bio
STATISTICAL ANALYSIS PLAN			

5.2.7 Inexact Values

In the case where a safety laboratory variable is recorded as “> x”, “≥ x”, “< x” or “≤ x”, a value of x will be taken for analysis purposes.

5.2.8 Change from Baseline

Change from baseline in absolute terms is defined as the baseline value subtracted from the post-baseline value:

$$\text{Change from Baseline} = \text{Post-baseline Value} - \text{Baseline Value}$$

5.2.9 Electrocardiogram (ECG) Data

For ECG data recorded on continuous scales, if replicate / triplicate values are recorded at a time point, the mean or the replicates rounded to the nearest integer will be used for summarization. For overall interpretation if more than one value is recorded, the most severe (worst case) of the respective readings will be taken.

5.2.10 Columbia-Suicide Severity Rating Scale (C-SSRS)

The following outcomes are C-SSRS categories and have binary responses (yes / no). The categories have been re-ordered from the actual scale to facilitate the definition of composite endpoints:

Category 1	Wish to be Dead
Category 2	Non-specific Active Suicidal Thoughts
Category 3	Active Suicidal Ideation with Any Methods (Not Plan) without Intent to Act
Category 4	Active Suicidal Ideation with Some Intent to Act, without Specific Plan
Category 5	Active Suicidal Ideation with Specific Plan and Intent
Category 6	Preparatory Acts or Behaviour
Category 7	Aborted Attempt
Category 8	Interrupted Attempt
Category 9	Actual Attempt (non-fatal)

QMD Ref: Worldwide-TMP-ST-054-1.0_Effective: 12Aug2022	Governing QMD: Worldwide-SOP-ST-026
Confidentiality Statement This document is the property of Worldwide Clinical Trials Inc. and may not be duplicated, copied, altered or removed from company without prior approval from Worldwide Quality Assurance or in compliance with Worldwide Standard Operating Procedures.	

Worldwide Clinical Trials Controlled Quality Management Document			
		Sponsor:	MTR-601-NHV-101
		Protocol Number:	Motric Bio
STATISTICAL ANALYSIS PLAN			

Category 10	Completed Suicide
-------------	-------------------

Suicidal Ideation since baseline – A “yes” answer at any time during double blind treatment to any one of the 5 suicidal ideation questions (categories 1-5) on the C-SSRS.

Suicidal Behaviour since baseline – A “yes” answer at any time during double blind treatment to any one of the 5 suicidal behaviour questions (categories 6-10) on the C-SSRS.

There will be no imputation of missing data for C-SSRS.

5.2.11 Unscheduled Visits

Only scheduled post-baseline laboratory and vital signs values will be tabulated unless otherwise stated. Post-baseline repeat / unscheduled assessments will be included in all listings in the relevant appendices to the CSR.

5.2.12 Pharmacokinetic Parameters

The following plasma PK parameters will be calculated for MRT-601 after single ascending doses (SAD):

Parameter	Definition
C_{max}	Maximum observed plasma concentration
T_{max}	Time of the maximum plasma concentration
AUC_{0-24}	Area under the plasma concentration-time curve from time-zero to 24 h postdose
AUC_{last}	Area under the plasma concentration-time curve from time-zero to the time of the last quantifiable concentration; calculated using the linear trapezoidal rule
AUC_{inf}	Area under the plasma concentration-time curve from time-zero extrapolated to infinity; calculated as: $AUC_{inf} = AUC_{last} + C_{last}/\lambda_z$ Note: Additional criteria for reporting AUC_{inf} are summarized in Section 5.14
$AUC_{Extrap} (\%)$	Percentage of AUC_{inf} based on extrapolation; calculated as: $AUC_{Extrap} = 100 \times [1 - (AUC_{last}/AUC_{inf})]$
λ_z (Lambda-z, k_{el})	Apparent elimination rate constant; calculated as the negative slope of the linear regression through the terminal log-linear segment of the plasma concentration-time curve Note: Additional criteria for reporting λ_z are summarized in Section 5.14

QMD Ref: Worldwide-TMP-ST-054-1.0_Effective: 12Aug2022	Governing QMD: Worldwide-SOP-ST-026
Confidentiality Statement This document is the property of Worldwide Clinical Trials Inc. and may not be duplicated, copied, altered or removed from company without prior approval from Worldwide Quality Assurance or in compliance with Worldwide Standard Operating Procedures.	

Worldwide Clinical Trials Controlled Quality Management Document			
		Sponsor:	MTR-601-NHV-101
		Protocol Number:	Motric Bio
STATISTICAL ANALYSIS PLAN			

Parameter	Definition
$T_{1/2}$	Observed terminal elimination half-life; calculated as: $T_{1/2} = \ln(2)/\lambda_z$
CL/F	Apparent total body clearance after extravascular administration, calculated as: $CL/F = \text{Dose}/AUC_{inf}$, where F is the bioavailability
V_z/F	Apparent volume of distribution after extravascular administration, calculated as: $V_z/F = \text{Dose}/(AUC_{inf} \times \lambda_z)$, where F is the bioavailability
C_{last}	Last observed quantifiable plasma concentration
T_{last}	Time of the last observed quantifiable plasma concentration

The following plasma PK parameters will be calculated for MRT-601 after multiple ascending doses (MAD) for Day 1 and Day 7:

Parameter	Definition
C_{max}	Maximum observed plasma concentration
T_{max}	Time of the maximum plasma concentration
AUC_{0-12} (AUC_{tau})	The area under the plasma concentration-time curve from time-zero to 12 hours postdose, calculated by the linear trapezoidal method (Cohorts 1 and 2)
AUC_{0-24} (AUC_{tau})	The area under the plasma concentration-time curve from time-zero to 24 hours postdose (24 h = dosing interval), calculated by the linear trapezoidal method (predose samples collected on Days 2 and 8 will be used as Day 1, 24 h and Day 7, 24 h samples for this calculation)

The following plasma PK parameters will be calculated for MRT-601 after multiple ascending doses (MAD) for Day 14:

Parameter	Definition
$C_{max,ss}$	Maximum observed plasma concentration
$T_{max,ss}$	Time of the maximum plasma concentration

QMD Ref: Worldwide-TMP-ST-054-1.0_Effective: 12Aug2022	Governing QMD: Worldwide-SOP-ST-026
Confidentiality Statement This document is the property of Worldwide Clinical Trials Inc. and may not be duplicated, copied, altered or removed from company without prior approval from Worldwide Quality Assurance or in compliance with Worldwide Standard Operating Procedures.	

Worldwide Clinical Trials Controlled Quality Management Document			
		Sponsor:	MTR-601-NHV-101
		Protocol Number:	Motric Bio
STATISTICAL ANALYSIS PLAN			

Parameter	Definition
AUC_{τ}	The area under the plasma concentration-time curve over the 24 h dosing interval, calculated by the linear trapezoidal method
C_{avg}	Average plasma concentration over the 24 h dosing interval, calculated as: $C_{avg} = AUC_{\tau}/\tau$
C_{last}	Last quantifiable plasma concentration
T_{last}	Time of the last quantifiable plasma concentration
CL_{ss}/F	The apparent total clearance at steady-state after extravascular administration, calculated as: $CL_{ss}/F = \text{Dose}/AUC_{\tau}$, where F is the bioavailability
V_z/F	The apparent volume of distribution at steady-state after extravascular administration, calculated as: $V_z/F = \text{Dose}/(AUC_{\tau} \times \lambda_z)$, where F is the bioavailability
R_{AUC}	Accumulation ratio of AUC_{τ} , calculated as: $AUC_{\tau} (\text{Day 14})/AUC_{0-24} (\text{Day 1})$ for Cohorts 3 onward only
$R_{C_{max}}$	Accumulation ratio of C_{max} , calculated as: $C_{max} (\text{Day 14})/ C_{max} (\text{Day 1})$

The following urine PK parameters will be calculated for MRT-601 (SAD, MAD, Day 1, 7, and 14):

Parameter	Definition
-----------	------------

QMD Ref: Worldwide-TMP-ST-054-1.0_Effective: 12Aug2022	Governing QMD: Worldwide-SOP-ST-026
Confidentiality Statement This document is the property of Worldwide Clinical Trials Inc. and may not be duplicated, copied, altered or removed from company without prior approval from Worldwide Quality Assurance or in compliance with Worldwide Standard Operating Procedures.	

Worldwide Clinical Trials Controlled Quality Management Document			
		Sponsor:	MTR-601-NHV-101
		Protocol Number:	Motric Bio
STATISTICAL ANALYSIS PLAN			

Cum_Ae	Cumulative amount of drug excreted in urine across each collection interval (0-4, 0-8, 0-12, etc) Calculated through 96 h for SAD and MAD Day 14 Calculated through 24 h for MAD Days 1 and 7
Total Ae	Total amount of drug excreted in urine over the entire collection interval (0-96 h) Calculated through 96 h for SAD and MAD Day 14 Calculated through 24 h for MAD Days 1 and 7
Fe	Fraction of dose excreted in urine for each collection interval, calculated as: $Fe = Ae / \text{dose administered}$ Calculated through 96 h for SAD and MAD Day 14 Calculated through 24 h for MAD Days 1 and 7
Fe (%)	Percent of dose excreted in urine for each collection interval, calculated as: $Fe\% = Ae / \text{dose administered} \times 100$
Cum_Fe (%)	Cumulative percent of dose excreted in urine across each collection interval (0-4, 0-8, 0-12, etc) Calculated through 96 h for SAD and MAD Day 14 Calculated through 24 h for MAD Days 1 and 7
Total Fe (%)	Total percent of dose excreted in urine over the entire collection interval (0-96 h), calculated as: $\text{Total Fe}\% = \text{Total Ae} / \text{dose administered} \times 100$ Calculated through 96 h for SAD and MAD Day 14 Calculated through 24 h for MAD Days 1 and 7
CL _r	Renal clearance, calculated as: SAD: $CL_r = \text{Total Ae} / AUC_{inf}$ MAD: $CL_r = Ae_{0-24} / AUC_{tau}$ (Day 14 only)

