1.2. Study Schema

SAD and MAD Schematic:

Motric Bio Study Scheme: Cohorts of 8 participants (6 MTR-601 and 2 placebo) will be sequentially enrolled following evaluation of safety and tolerability (S and T) by a Safety Review Committee (SRC). The SRC will determine whether any dose is safe and tolerable by evaluation of aggregate clinical, laboratory, ECG, echocardiography, spirometry, renal/urinary ultrasonography and PK (as available) data. The Single Ascending Dose (SAD) cohorts will begin dosing with 2 sentinel participants (1:1 - MTR-601: Placebo) followed 72 hours later by dosing the remainder of the cohort (5:1 - MTR-601: Placebo). Dosing will be performed after a standard breakfast, in all but one cohort, as preclinical studies indicated food enhanced exposure. The second SAD cohort will receive two doses of study drug – the first dose will be after overnight fasting and the second dose, following a washout period, after a standard breakfast. The Multiple Ascending Dose (MAD) cohorts will not begin until at least the SAD level 2 two-dose cohort has been completed and will not have sentinel dosing. MAD dosing will be daily for 14 days.

Abbreviations: AE = adverse event; CK-MB = creatinine kinase heart; CK-MM = creatinine kinase skeletal muscle; CRU = clinical research unit; D = Day; Hep = hepatitis; HIV = human immunodeficiency virus; LVEF = left ventricular ejection fraction; PCR = polymerase chain reaction; PK = pharmacokinetics; SARS-CoV-2 = severe acute respiratory syndrome coronavirus 2.

Note: When several assessments overlap, the suggested sequence of events will be as follows: ECG, vital sign collection, PK sample collection, laboratory blood sample collections, spirometry, dynamometry, urinalysis sample collection, and biopsy such that PK sample collection will be drawn as close to the nominal collection time point as possible.

- a. Height measured only at screening.
- b. To be performed as part of check-in procedures, prior to other Day -1 activities
- c. Urine drug screen for cotinine, alcohol, and drugs of abuse.
- d. Laboratory assessments will include serum chemistry, hematology, liver function tests, coagulation, and creatinine kinase (CK-MM and CK-MB). eGFR will use CKD-EPI calculation. For Cohort 4 only. Cystatin C will be measured on Day 1 at 4 and 12 hours post dose, and on Day 2.

- e. FSH testing for postmenopausal females only.

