2.3. Nonclinical Studies and Interim Safety Analysis

Refer to the Investigator's Brochure (IB) or MTR-601 regarding nonclinical study data.

An unblinded interim safety analysis of SAD cohorts 1-4 and MAD cohorts 1-3 was performed to support further dose escalation above the 1/10th rat 28-day NOAEL level (where MAD dosing had been capped by the FDA). The key conclusions from that interim analysis were:

- In either single doses (10, 20, 40 and 80 mg) or repeat daily doses (10 and 20 mg for 14 days) MTR-601 did not demonstrate pharmacodynamic evidence of decreased muscle strength. This is likely because the achieved muscle concentrations (≤ 937 ng/mL) were below the estimated target for efficacy ($\geq 3,000$ ng/dL). Further dose escalation is required to adequately characterize MTR-601's pharmacodynamic effect.
- In both single and multiple doses, MTR-601 plasma pharmacokinetics were consistent and predictable, with linear dose-exposure proportionality, and modest (<2 -fold) accumulation at steady state. At the 20 mg level, steady state exposure (C_{max} and AUC_{0-24}) was approximately 1/15th of the NOAEL. MTR-601's well-behaved pharmacokinetics allows for reliable prediction of exposure for careful, continued dose escalation.
- In both single and multiple doses, MTR-601 was safe and very well tolerated, with no treatment-related AEs, and no clinically significant laboratory, ECG, or vital sign abnormalities. There were no MTR-601 associated abnormalities in plasma or urine markers of kidney function, and no objective or subjective evidence of urinary obstruction. This very good safety profile justifies continued dose escalation to more fully characterize MTR-601's clinical profile.

The findings of the interim safety evaluation support continued dose escalation to more fully characterize the PK, PD and safety of MTR-601.

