5.14 Pharmacokinetic Analyses

5.14.1 Concentration-Time Data

5.14.1.1 Plasma

MRT-601 plasma concentration-time data will be tabulated by nominal time and treatment (dose level) for SAD and by nominal time, treatment (dose level), and study day for MAD using descriptive statistics. For presentation of the individual data and summary statistics, concentrations below the limit of quantitation (BLQ) will be set to zero. Nominal and relative time will be presented in hours.

MRT-601 samples will be collected at:

SAD: 0 (pre-dose) and at 0.25, 0.50, 1, 1.5, 2, 4, 6, 8, 12, 24, 48, 72, and 96 hours post-dose.

SAD (2 dose, food effect): 0 (pre-dose 1) and at 0.25, 0.50, 1, 1.5, 2, 4, 6, 8, 12, 24, 48, 72, and 96 hours postdose

MAD, Day 1: 0 (predose) and at 0.25, 0.50, 1, 1.5, 2, 4, 6, 8, and 12 hours postdose for Cohorts 1 and 2. A 24 hour sample (Day 2, predose) was added for Cohort 3 onward.

QMD Ref: Worldwide-TMP-ST-054-1.0_Effective: 12Aug2022	Governing QMD: Worldwide-SOP-ST-026
Confidentiality Statement This document is the property of Worldwide Clinical Trials Inc. and may not be duplicated, copied, altered or removed from company without prior approval from Worldwide Quality Assurance or in compliance with Worldwide Standard Operating Procedures.	

Worldwide Clinical Trials Controlled Quality Management Document			
		Sponsor:	MTR-601-NHV-101
		Protocol Number:	Motric Bio
STATISTICAL ANALYSIS PLAN			

MAD Day 7: 0 (predose) and at 0.25, 0.50, 1, 1.5, 2, 4, 6, 8, and 12 hours postdose for Cohorts 1 and 2. A 24 hour sample (Day 8, predose) was added for Cohort 3 onward.

MAD Day 14: 0 (pre-dose) and at 0.25, 0.50, 1, 1.5, 2, 4, 6, 8, 12, 24, 48, 72, and 96 hours post-dose.

Mean plasma concentration-time data will be presented graphically on linear and semi-logarithmic scales using nominal times. Individual subject concentration-time data will be presented graphically on linear and semi-logarithmic scales using actual times. For individual subject concentration-time data, spaghetti plots (all subjects in one plot per treatment) and all treatments in one plot for each subject will be created.

For SAD, mean profiles and spaghetti plots will be created.

For SAD (food effect): mean profiles, spaghetti plots, and individual plots (fed vs. fasted) will be created.

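### The linear trapezoidal rule across 12- and 24-hour sampling gaps overstates SAD AUC by a few percent where late samples are quantifiable; linear-up/log-down removes most of the error at little cost

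*SAP*

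**What the plan says.** For the SAD part, SAP 5.2.12 defines AUClast as "Area under the plasma concentration-time curve from time-zero to the time of the last quantifiable concentration; calculated using the linear trapezoidal rule". The extrapolated area, AUCinf, is AUClast plus Clast/λz. CL/F and Vz/F are computed from AUCinf, and so is SAD renal clearance (total Ae divided by AUCinf). SAD AUC0-24 is listed with no integration rule.

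The SAP 5.14.1.1 sampling times are "SAD: 0 (pre-dose) and at 0.25, 0.50, 1, 1.5, 2, 4, 6, 8, 12, 24, 48, 72, and 96 hours post-dose". The gaps after 12 h are therefore one of 12 h and three of 24 h.

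For MAD Day 14, SAP 5.2.12 defines AUCtau as "The area under the plasma concentration-time curve over the 24 h dosing interval, calculated by the linear trapezoidal method". It crosses only the 12 h gap.

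Three further statements bear on the point:
- Protocol 2.3 reports that accumulation at steady state was modest, below 2-fold. Protocol 1.2 gives the dosing interval: "MAD dosing will be daily for 14 days".
- SAP 5.14.2 treats concentrations below the limit of quantitation (BLQ) after the last quantifiable sample as missing, so AUClast stops at that sample.
- SAP section 6 records that the sponsor team has reviewed data unblinded.

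Neither document gives a half-life, an absorption rate or an LLOQ. The text available for review plans no log-trapezoidal rule and no sensitivity analysis of the integration method.

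**The concern.** A straight line between two points on a convex falling curve lies above the curve, so the linear rule overstates the area in every late gap. The error is one-sided, and more subjects do not average it out. Low accumulation on daily dosing suggests that a 24 h gap spans at least one half-life, which is long enough for the error to be visible.

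At stake is the accuracy of the SAD PK parameters, in a study where plasma and urine PK is the secondary objective. AUCinf would be too high, and CL/F, Vz/F and SAD renal clearance too low. MAD AUCtau carries a smaller error. SAD CL/F and MAD CLss/F could then differ slightly because of the integration rule, even if the kinetics were linear and unchanged over time.

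**Working it through.** The documents give no bias figure to reproduce, so the error was calculated from their sampling times under stated assumptions.

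**Inputs from the documents:** the SAP 5.14.1.1 sampling times, the linear rule of 5.2.12, the BLQ handling of 5.14.2, accumulation below 2-fold (Protocol 2.3) and a 24 h dosing interval.

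**Assumed, because not given:** one compartment with first-order absorption, half-life 6-24 h, ka 0.5-2/h, LLOQ at 0, 1% or 5% of Cmax.

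**Step 1, half-life.** Accumulation is R = 1/(1 − 2^(−24/t½)). This gives R = 2.00 at 24 h, 1.33 at 12 h and 1.14 at 8 h, so R below 2 means an effective half-life below 24 h. It does not bound the terminal half-life.

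**Step 2, a single 24 h gap.** With x = ln2 × 24/t½, linear area/true area = (x/2)(1 + e^−x)/(1 − e^−x). At t½ 12 h, x = 1.386 and the ratio is 0.693 × 1.25/0.75 = 1.155. The overstatement within one gap is 4% at 24 h, 9% at 16 h, 15.5% at 12 h, 34% at 8 h and 57% at 6 h. Late gaps hold only part of the total area, so these are not errors in AUC.

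**Step 3, the whole profile.** C(t) is proportional to e^(−kt) − e^(−ka·t), sampled at the SAP times. The linear sum is compared with the exact integral (1 − e^(−kT))/k − (1 − e^(−ka·T))/ka. Ranges are over ka 0.5-2/h.

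| t½ | AUClast, all quantifiable to 96 h | AUCinf, LLOQ 1% of Cmax (last sample) | AUCinf, LLOQ 5% of Cmax (last sample) | MAD AUCtau | AUClast, linear-up/log-down |
|---|---|---|---|---|---|
| 6 h | +7.0 to +7.8% | +3.1 to +3.2% (24 h) | +3.1 to +3.2% (24 h) | +3.3 to +3.4% | −0.4 to −0.9% |
| 8 h | +6.5 to +7.0% | +5.9 to +6.3% (48 h) | +1.9 to +2.1% (24 h) | +2.3 to +2.4% | −0.3 to −0.7% |
| 12 h | +4.9 to +5.0% | +4.7 to +4.8% (72 h) | +3.9 to +4.0% (48 h) | +1.1 to +1.3% | −0.2 to −0.5% |
| 16 h | +3.5 to +3.6% | +3.5% (96 h) | +2.5 to +3.2% (48 or 72 h) | +0.6 to +0.8% | −0.1 to −0.4% |
| 24 h | +2.0% | +1.8 to +1.9% (96 h) | +1.8 to +1.9% (96 h) | +0.2 to +0.4% | −0.1 to −0.3% |

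Outside this grid:
- When the last quantifiable sample is at 12 h (t½ 4 h, LLOQ 5% of Cmax), the AUCinf error is −0.7% to +0.5%.
- At ka 0.3/h, t½ 6 h and LLOQ 1% of Cmax it reaches +7.9%. At ka 0.3/h and t½ 4 h the linear-up/log-down error reaches −1.8%.
- Biexponential profiles with AUC accumulation of 1.4-1.9 and terminal half-life up to 40 h give AUCinf +2.8% to +3.7% with the linear rule.

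**Step 4, clearance.** CL/F = Dose/AUCinf, so +7.8% in AUCinf is 1/1.078 − 1 = −7.2% in CL/F. For SAD against MAD at t½ 12 h and ka 1/h, 1.012/1.049 − 1 = −3.5%. With every sample quantifiable, SAD CL/F falls below MAD CLss/F by 1.5% to 4.4%. With the last SAD sample at 24 h, the two agree within about 0.4%.

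**Step 5, planned comparisons.** Suppose the last quantifiable time lengthens with dose, so that the AUC error rises from +3.1% to +7.8% (t½ 6 h) or from +1.9% to +7.0% (t½ 8 h) over 10-160 mg. The power-model slope then shifts by ln(1.078/1.031)/ln16 = 0.016 or ln(1.070/1.019)/ln16 = 0.018. The MAD AUC accumulation ratio is almost unchanged (1.361 true against 1.362 linear at t½ 12 h, ka 1/h).

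**The case against.** The strongest reply is that this is a preference between two accepted rules. The linear rule is explicit and prespecified. Its largest errors arise at short half-lives, where late samples are least likely to be quantifiable. At t½ 6 h, concentrations at 48 h are already below 1% of Cmax. If the LLOQ is at that level, AUClast ends at 24 h, no 24 h gap is used, and the error is about 3%, close to that of MAD AUCtau. The study is descriptive, and no planned decision is shown to change:
- The exposure cap uses Cmax and AUC0-24, which cross no 24 h gap.
- The bias largely cancels in the fasted/fed ratio when half-life and last quantifiable time match.
- The SAP plans no formal comparison of SAD CL/F with MAD CLss/F.

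Most of this stands. It limits the size and consequence of the point, but not its direction where samples after 24 h are quantifiable. Nor does it explain why a rule with a known one-sided error should be kept when the same samples support a better one.

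The objection to changing method after unblinded interim review also has weight. It is a reason to show both sets of values.

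A reader might infer that SAD AUC is certainly overstated by 7-8%, or that SAD and MAD clearance must differ by several percent. The documents do not support either. The first needs a short half-life and quantifiable samples to 96 h. The second describes only the upper part of a range that starts near zero.

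**Conclusion.** The point holds as a minor, conditional one. Where SAD samples after 24 h are quantifiable, the plan as written overstates AUClast and AUCinf and understates CL/F, Vz/F and SAD renal clearance. Under one-compartment kinetics with ka 0.5-2/h and half-life 6-24 h, the AUC error is about +2% to +8% if everything to 96 h is quantifiable, and about +2% to +6% with an LLOQ of 1-5% of Cmax. It is near zero if the last quantifiable sample is at 12 h. MAD AUCtau is overstated by about 0.2% to 3.4%, so the rule alone can separate SAD CL/F from MAD CLss/F by about 0-4.5%.

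These sizes rest on assumed half-life, absorption rate and LLOQ, and the reported accumulation bounds only an effective half-life. No main conclusion of the study is shown to turn on the choice of rule. The case for acting is that the improvement is cheap.

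**What to change.** In SAP 5.2.12, specify linear-up/log-down for all plasma AUCs in both parts, including SAD AUC0-24, which has no stated rule. Make the change by SAP amendment approved before database lock, as SAP section 5 requires, and apply it to all cohorts, including completed ones. Because unblinded interim data have been reviewed, state the reason for the change and report the linear-rule values as a sensitivity analysis.

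On the same samples, the remaining error is about −0.1% to −1.8% in the one-compartment runs and +0.5% to +1.5% in the biexponential ones. No new data are needed. The cost is an amended phrase, a re-run of the noncompartmental analysis and one additional output. Early-cohort AUCs will come out a few percent below the interim values if those used the linear rule, and the report should say so.

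### MAD Day 14 fraction excreted in urine sets 96 h of urine from 14 daily doses against one dose; only the 0-24 h value is a fraction of a dose

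*SAP*

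**What the plan says.** The urine table in SAP 5.2.12 sets two collection windows. For the amount and fraction parameters, one is "Calculated through 96 h for SAD and MAD Day 14" and the other is "Calculated through 24 h for MAD Days 1 and 7". Fe is described as "Fraction of dose excreted in urine for each collection interval, calculated as" Ae over the dose administered. Total Fe (%) is "Total percent of dose excreted in urine over the entire collection interval (0-96 h), calculated as" Total Ae over the dose administered, times 100. Fe (%) has no window of its own but uses the same divisor.

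SAP 5.14.1.2 confirms that Day 14 urine is collected in intervals up to 72-96 h after the dose. The SAP introduction gives MAD dosing as daily for 14 days.

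The last row, "Renal clearance, calculated as", uses Total Ae (0-96 h) over AUCinf for SAD, but Ae over 0-24 h divided by AUCtau for MAD Day 14. The MAD version pairs equal intervals; the SAD version does not.

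**The concern.** At steady state, the drug eliminated over one dosing interval balances one dose. Urine collected after that interval, with no further dosing, is washing out the amount accumulated over the whole course. Adding it to the numerator while keeping one dose in the denominator inflates the fraction.

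The SAP respects this balance elsewhere. CLss/F is Dose/AUCtau, and MAD renal clearance is Ae0-24/AUCtau. Hence (Ae0-24/Dose) × (Dose/AUCtau) equals the renal clearance exactly. With the 96 h Total Fe the identity fails, so three Day 14 outputs for the same subject cannot be reconciled.

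SAP 5.3 summarises MAD PK parameters by dose level and study day, so Days 1, 7 and 14 will be read against each other. A reader of the planned MAD urine tables (14.4.5.2, 14.4.6.2, 14.4.7.2 and 14.4.9.2) could take the Day 14 figure as a change in renal handling, or as a larger share of the dose leaving unchanged than is true. Urine PK is part of the secondary objective.

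**Working it through.** The plan states no numerical result for these parameters, so there is no figure to reproduce. The check is a mass balance.

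**Inputs**
- Dosing interval 24 h, 14 doses (SAP introduction).
- Day 14 urine to 96 h (SAP 5.2.12 and 5.14.1.2).
- Accumulation below 2-fold at steady state, and plasma kinetics "with linear dose-exposure proportionality" (protocol 2.3).
- Half-life: not given. Assumed range 8 to 24 h, one compartment, linear, k = ln 2 / half-life.

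**MAD Day 14.** Let f be the true fraction of a dose excreted unchanged. With rapid absorption, the amount in the body just after the Day 14 dose is Dose × R, where R = 1/(1 − e^(−24k)). Urine over 0-T then holds f × Dose × R × (1 − e^(−kT)).
- T = 24 h: Ae/Dose = f. This is the matched fraction.
- T = 96 h: Ae/Dose = f × (1 − e^(−96k))/(1 − e^(−24k)).

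**SAD renal clearance.** Ae0-96/AUCinf divided by the true value is 1 − e^(−96k).

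| Half-life | R | Day 14 Total Fe / true | SAD CLr / true |
|---|---|---|---|
| 8 h | 1.14 | 0.9998/0.875 = 1.14 | 0.9998 |
| 12 h | 1.33 | 0.9961/0.75 = 1.33 | 0.996 |
| 18 h | 1.66 | 0.9752/0.6031 = 1.62 | 0.975 |
| 24 h | 2.00 | 0.9375/0.5 = 1.875 | 0.9375 |

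R = 2 corresponds to a half-life of 24 h, so the last row is the ceiling under the reported accumulation.

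**Sensitivity to absorption.** Summing all 14 doses with first-order absorption at 0.3, 1 and 3 per hour, accumulation of 2 occurs at half-lives of 20.5, 23.0 and 23.7 h. Total Fe is then 1.82, 1.86 and 1.87 times the true value, and SAD CLr is 0.956, 0.943 and 0.939 times the true value. The ceiling is therefore about 1.8 to 1.9 for Fe, and a shortfall of about 4-6% for CLr. At that ceiling, reported Total Fe would pass 100% if the true fraction exceeded 1/1.875 = 53% to 1/1.82 = 55%.

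**Across study days at a 24 h half-life, constant renal handling (multiples of f)**
- Day 1, 0-24 h: 1 − 2^(−1) = 0.50
- Day 7, 0-24 h: 1 − 2^(−7) = 0.99
- Day 14, 0-24 h: 1 − 2^(−14) = 1.00
- Day 14, 0-96 h: 1.875

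The step from Day 1 to Day 7 is ordinary accumulation. Almost all of the step from Day 7 to the Day 14 total comes from the longer window.

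**The case against.** **The valid figure is already planned.** Cum_Fe (%) is reported at each collection boundary and Day 14 has a 12-24 h collection, so Day 14 Ae0-24/dose will appear in Table 14.4.7.2. This stands. The fault lies in the values after 24 h and in the total, and the total is the one labelled as the overall result.

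**The divisor does not literally say one dose.** True, but dividing by all 14 doses would also be mismatched, because the Day 14 collection starts only at the last dose.

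**The whole rise from Day 1 to Day 14 might be thought spurious.** It is not. Day 1 precedes steady state, so even the corrected Day 14 value exceeds Day 1 by the accumulation ratio. Only the Day 7 to Day 14 contrast is created by the window.

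**The SAD clearance error might be put at 25% or 30%.** The 30% would come from the AUCinf extrapolation limit in SAP 5.14.2. A 25% shortfall needs a 48 h half-life, hence R = 1/(1 − 2^(−0.5)) = 3.4. A 30% shortfall needs about 55 h, hence R = 1/(1 − 0.3^(1/4)) = 3.85. Both contradict the accumulation below 2-fold in protocol 2.3. The limit is a per-subject acceptance rule, not an expected bias. With 6 active subjects and an assumed CV of 20-30%, the standard error of a cohort mean is about 8-12% (20/√6 to 30/√6), so a 4-6% shift would hardly show.

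**A link to the urinary safety findings might be inferred.** The documents do not support it. Protocol 2.5 says the rat urinary signs are not expected in humans. Monitoring rests on IPSS, ultrasound, eGFR and the stopping rules, and the escalation cap uses plasma Cmax and AUC. None of these uses Fe or CLr.

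**Conclusion.** The Day 14 point holds. As defined, MAD Day 14 Fe, Fe (%) and Cum_Fe (%) beyond 24 h, and Total Fe (%), are not fractions of one dose, and nothing else in either document corrects this. The overstatement of the total runs from about 14% (half-life 8 h) to at most about 88% (24 h). The upper figure is a ceiling and should not be read as the expected error.

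The sizes rest on one-compartment linear kinetics and an assumed half-life. They also assume that the accumulation bound, observed at repeat doses of 10 and 20 mg, carries over to the higher MAD doses. The direction of the error does not depend on the exact half-life.

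The SAD clearance mismatch is real but minor: about 0.4% low at 12 h and 4-6% low at the accumulation bound. MAD renal clearance is correct as written. The consequence is confined to descriptive secondary PK output; no escalation or safety decision in the documents depends on it.

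**What to change.** - **MAD Day 14:** define Fe, Fe (%), Cum_Fe (%) and Total Fe (%) over 0-24 h only, as Ae0-24/dose. Report the 24-96 h collections as amounts (Ae, Cum_Ae) without dividing by dose. Correct the 0-96 h label on the total fraction, which already does not fit the 24 h window used for MAD Days 1 and 7.
- **SAD renal clearance:** define it as Ae0-t/AUC0-t over one common interval, and define that partial AUC, since AUC0-96 is not among the SAD parameters. This also avoids losing CLr when AUCinf fails its reporting criteria.
- **Before fixing t:** reconcile the last plasma sample of the SAD Level 2 fasted period, which is 72 h in the protocol (Table 2, plasma PK footnote) and 96 h in SAP 5.14.1.1.

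The cost is an edit to five rows of the SAP 5.2.12 urine table (Fe, Fe (%), Cum_Fe (%), Total Fe (%), CLr) and the matching output shells, made before database lock. No new samples are needed. Day 7 and Day 14 fractions then cover the same interval, and the Day 14 fraction agrees with CLss/F and renal clearance.
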